9.7.1.8.3 LABORATORY VALUES

Laboratory results will be summarized using Système International (SI) units, as appropriate. For all quantitative parameters, the actual value at each visit and the change from baseline to each postbaseline visit will be summarized using descriptive statistics. Qualitative parameters will be summarized using frequencies (number and percentage of subjects), and changes from baseline to each postbaseline visit will be reported using shift tables. Percentages will be based on the number of subjects with both nonmissing baseline and relevant postbaseline results.

Laboratory test results will be assigned a low/normal/high (LNH) classification according to whether the value was below (L), within (N), or above (H) the laboratory parameter's reference range. Within-treatment comparisons for each laboratory parameter will be based on shift tables that compare the baseline LNH classification to the LNH classification at each postbaseline visit.

Appendix 1 (Sponsor's Grading for Laboratory Values) presents the criteria that will be used to identify subjects with treatment-emergent markedly abnormal laboratory values (TEMAVs). Except for phosphate, a TEMA V is defined as a postbaseline value with an increase from baseline to a grade of 2 or higher. For phosphate, a TEMA V is defined as a postbaseline value with an increase from baseline to a grade of 3 or higher. The definition of TEMA V will be detailed in the SAP. When displaying the incidence of TEMAVs, each subject may be counted once in the laboratory parameter high and in the laboratory parameter low categories, as applicable.

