9.3.1 Inclusion Criteria

Subjects must meet all of the following criteria to be included in this study:

1. Male or female aged 12 years or older at the time of informed consent/assent
2. Have a diagnosis of epilepsy with POS with or without secondarily generalized seizures or PGTC seizures according to the International League Against Epilepsy (ILAE) Classification of Epileptic Seizures (1981)
3. Have been receiving a stable dosage of oral perampanel (8 to 12 mg/day) for at least 28 days before Day 1 in the Treatment Phase
4. Have been receiving a concomitant stable dosage of 1 to a maximum of 3 marketed AED(s) (regarding phenobarbital used as an AED, phenytoin, and carbamazepine, only one is allowed) for at least 28 days before Day 1 in the Treatment Phase. No change of dosing regimen for concomitant AED(s) is planned during the Treatment and Follow-up Phases.
5. Are considered reliable and willing to be available for the study period by the investigator, and are able to record seizures and report adverse events (AEs) by themselves or have a caregiver who can record seizures and report AEs for them

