9.5.1.5.3 STUDY-SPECIFIC ADVERSE EVENTS

In a non-clinical toxicity study of sodium sulphobutylether-beta-cyclodextrin (hereinafter “SBECD”), which is one of the additives in this study drug, vacuolation was observed in tubular epithelial cells, suggesting that patients with impaired renal function have a risk of SBECD accumulation (Luke, et al., 2010). In addition, there have been reports of anaphylaxis, possibly due to SBECD, with other formulations containing SBECD.

In this study, based on the above findings, adverse events associated with renal dysfunction, and adverse events associated with anaphylaxis will be handled as “adverse events of special interest (AESIs)” and recorded in the CRF.

For the procedures for reporting adverse events of special interest, see Section 9.5.4.3.2

1. Adverse Events Associated With Renal Dysfunction

If an adverse event associated with renal dysfunction occurs, and does not resolve at the time point when the Follow-up Phase is completed, the investigator will monitor the subject for 14 days from the follow-up visit, regardless of severity, and will continue following up the subject as needed until resolution of the event or, if resolution is unlikely, until stabilization of the symptom or sign. During this period, the subject will be followed up continuously by renal function monitoring at unscheduled visits (eg, once weekly, or at a frequency deemed necessary by the investigator).

2. Adverse Events Associated With Anaphylaxis

In the event of an adverse event associated with anaphylaxis, the investigator will take the following responsive actions:

- Take the first response, for example, by immediately referring the subject to an appropriate clinical department;
- Make a decision regarding whether or not to continue administration of the study drug to the subject, based on advice from the physician in the above-mentioned department;
- In the event of an adverse event associated with anaphylaxis while continuing intravenous administration of the study drug, discontinue the administration. In the event of any symptom or sign that is suspected of anaphylaxis while continuing intravenous administration of the study drug, careful judgment will be exercised in determining whether or not to continue the administration.

The follow-up of anaphylaxis will be continued until resolution of the event or, if resolution is unlikely, until stabilization of the symptom or sign.

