9.5.4.3.2 REPORTING OF STUDY-SPECIFIC EVENTS

In this study, adverse events associated with renal dysfunction and adverse events associated with anaphylaxis will be handled as “adverse events of special interest (AESIs)”

(see Section 9.5.1.5.3).

If an adverse event of special interest associated with renal dysfunction, with an elevated creatinine level $>3\times$ the upper limit of normal (ULN), or an adverse event associated with anaphylaxis (regardless of severity) is observed, it will be reported according to the procedures specified in “Reporting of Serious Adverse Events” (Section 9.5.4.1) even if the AEs do not meet serious criteria. If the event does not meet the definition of a SAE, it must still be reported using the SAE form and in an expedited manner but should be noted as nonserious on the SAE form and the Adverse Event CRF.

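### The creatinine TEMAV rule uses only multiples of ULN, so the TEMAV incidence can miss a doubling or tripling of a subject's own creatinine, although renal dysfunction is an AESI

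*Protocol*

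**What the plan says.** Protocol section 9.7.1.8.3 states that Appendix 1 "presents the criteria that will be used to identify subjects with treatment-emergent markedly abnormal laboratory values (TEMAVs"), and then gives the rule: "Except for phosphate, a TEMA V is defined as a postbaseline value with an increase from baseline to a grade of 2 or higher". In the creatinine row of Appendix 1 every grade is a multiple of ULN: grade 1 above ULN to 1.5×, grade 2 above 1.5× to 3.0×, grade 3 above 3.0× to 6.0×, grade 4 above 6.0×. The row contains no multiple of the subject's own baseline.

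The same section plans two other laboratory outputs. Results are classed low, normal or high (LNH) "according to whether the value was below (L), within (N), or above (H) the laboratory parameter's reference range", and shifts in class are tabulated. In addition, "For all quantitative parameters, the actual value at each visit and the change from baseline to each postbaseline visit will be summarized using descriptive statistics". Section 9.7.1.8 names minimum and maximum among the descriptive statistics.

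Renal dysfunction is one of two AESI categories (section 9.5.1.5.3). The stated reason is the excipient SBECD, for which "vacuolation was observed in tubular epithelial cells" in a non-clinical toxicity study. Section 9.5.4.3.2 adds expedited reporting of a renal AESI "with an elevated creatinine level" above 3×ULN. Entry is open to subjects "Male or female aged 12 years or older at the time of informed consent/assent" (section 9.3.1).

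**The concern.** In the TEMAV rule, an increase from baseline means a rise in grade, not a rise in the subject's own value. Because the creatinine grades are anchored only to ULN, the rise needed for a TEMAV depends on where the subject started: the lower the baseline, the larger the proportional rise that goes uncounted.

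That matters more here than in a trial without a renal question. The exclusion criteria remove clinically significant renal disease and clinically significant laboratory abnormalities, so most subjects should enter at or below ULN, where the rule is least sensitive to proportional change. There are 20 subjects and two scheduled postbaseline laboratory draws (Day 4 predose and Follow-up). The trial could report no creatinine TEMAV although a subject's creatinine had doubled, and a reader would take that zero as reassurance on the AESI.

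**Working it through.** **Inputs.** TEMAV threshold: above 1.5×ULN (section 9.7.1.8.3 with Appendix 1). LNH threshold for high: above 1×ULN (section 9.7.1.8.3). The baseline fraction b = baseline/ULN is not in the protocol and is varied as an assumption from 0.30 to 0.90.

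**Formulas.** After an f-fold rise the value is b×f in units of ULN.
- A TEMAV requires b×f > 1.5, so f > 1.5/b.
- A shift from normal to high requires b×f > 1, so f > 1/b.
- A doubling is not a TEMAV if 2b ≤ 1.5, that is b ≤ 0.75. It stays normal if 2b ≤ 1, that is b ≤ 0.50.
- A tripling is not a TEMAV if 3b ≤ 1.5, that is b ≤ 0.50. It stays normal if 3b ≤ 1, that is b ≤ 0.33.

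**Results.**

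| b | TEMAV above (fold) | High above (fold) | Doubling: ×ULN, outcome | Tripling: ×ULN, outcome |
|---|---|---|---|---|
| 0.30 | 5.00 | 3.33 | 0.60, normal | 0.90, normal |
| 0.40 | 3.75 | 2.50 | 0.80, normal | 1.20, grade 1, high |
| 0.50 | 3.00 | 2.00 | 1.00, normal | 1.50, grade 1, high |
| 0.60 | 2.50 | 1.67 | 1.20, grade 1, high | 1.80, TEMAV |
| 0.75 | 2.00 | 1.33 | 1.50, grade 1, high | 2.25, TEMAV |
| 0.90 | 1.67 | 1.11 | 1.80, TEMAV | 2.70, TEMAV |

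**What the other outputs add.**
- *LNH shift table.* It catches some rises that the TEMAV misses, but it does not grade them by size. A move from 0.95 to 1.05×ULN (1.05/0.95 = 1.1-fold) and one from 0.40 to 1.20×ULN (3-fold) are both a single shift from normal to high, and neither is a TEMAV.
- *Maximum change from baseline.* This is an absolute difference. A rise from 0.40 to 0.80×ULN and one from 0.90 to 1.30×ULN both differ by 0.40×ULN, yet the first is 2.0-fold and the second 1.30/0.90 = 1.4-fold. The maximum also does not say how many subjects had a large rise.

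**Sensitivity to the ULN (assumed values, not in the protocol).** Take a baseline of 0.5 mg/dL. With ULN 1.0 (b = 0.50), a doubling is ungraded and a tripling is grade 1; neither is a TEMAV. With ULN 0.7 (b = 0.71), a doubling is grade 1 and not a TEMAV, while a tripling is grade 2 and is a TEMAV. A lower age-specific ULN would narrow the gap but not close it.

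**The case against.** The strongest reply is that the protocol leaves detail of the TEMAV definition to the SAP, which is not shown and might add a baseline-relative criterion. That possibility stands. But the protocol does not leave the criteria open: it names Appendix 1 as their source and prints the creatinine cutoffs. The point is about what it fixes, not what it omits.

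A second reply is that a flag for marked abnormality properly measures distance from the reference range, that the grading is stated to be CTCAE-based, and that nothing in the protocol contradicts it. This is fair. The rule is coherent; it simply does not answer how many subjects had a substantial rise in their own creatinine.

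Third, the other routes are not empty. The LNH table works at subject level and has a lower threshold than the TEMAV. With 20 subjects, the maximum change would show the largest absolute rise. AE recording (section 9.5.1.5.1) is not confined to abnormalities that lead to intervention: the investigator must assess all laboratory results and may record an AE on judgment. All of this stands and narrows the point.

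For the same reasons, three stronger readings should be resisted:
- A reader might infer that no subject-level signal appears until creatinine has risen several-fold. The LNH thresholds above contradict that.
- A reader might take the 3×ULN figure as the point at which a renal AESI begins. It governs expedited reporting only; section 9.5.1.5.3 sets no creatinine threshold for recording a renal AESI.
- A reader might translate a doubling into a stated loss of renal function, or assume that adolescents start far below ULN. The protocol supports neither: it gives no relation between creatinine and renal function, no ULN, and no statement on age-specific ranges.

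**Conclusion.** The narrower point holds. As defined, the creatinine TEMAV incidence misses a doubling at b ≤ 0.75 and a tripling at b ≤ 0.50. Of these, a doubling also stays normal in the LNH table at b ≤ 0.50 and a tripling at b ≤ 0.33. No planned output counts subjects by rise over their own creatinine, in a trial that made renal dysfunction an AESI.

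The thresholds follow from the protocol's own cutoffs by algebra. How many subjects would fall in the affected range depends on baseline fractions that are assumed here. This is a cheap improvement to the safety analysis, not an error that undermines the trial.

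**What to change.** In section 9.7.1.8.3 and Appendix 1, add a baseline-relative creatinine flag for analysis only: for example, any postbaseline value at least 1.5 times the subject's pre-infusion value. Report the number and percentage of subjects meeting it alongside the ULN-based TEMAV, and list those subjects with BUN and urinalysis results.

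Keep both criteria. For a subject starting above ULN the TEMAV can be the more sensitive one: at b = 1.2 it needs a rise above 1.5/1.2 = 1.25-fold. The factor 1.5 is a proposal, not a figure from the protocol for this purpose; what matters is that some multiple is fixed in advance. Expedited reporting and subject management stay as they are.

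The cost is one sentence and one programming line on values already scheduled for collection. The downside is a few additional flags from ordinary variation at low baselines, which the listing lets a reader judge case by case.

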9.7.1.8.4 VITAL SIGNS AND WEIGHT

Descriptive statistics for vital sign parameters (ie, systolic and diastolic blood pressure, pulse, respiratory rate, temperature) and weight; and changes from baseline will be presented by visit.

9.7.1.8.5 ELECTROCARDIOGRAMS

Shift tables will present changes from baseline in ECG interpretation (categorized as normal; abnormal, not clinically significant; and, abnormal, clinically significant) by visit.

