(Subject must be on a stable dose of the same oral contraceptive product for at least 28 days before Day 1 in the Treatment Phase and throughout the entire study period, and for 28 days after the last dose of the study drug)
 - have a vasectomized partner with confirmed azoospermia.
 - Do not agree to use a highly effective method of contraception (as described above) throughout the entire study period and for 28 days after the last dose of the study drug.

It is permissible that if a highly effective method of contraception is not appropriate or acceptable to the subject, then the subject must agree to use a medically acceptable method of contraception, ie, double-barrier methods of contraception such as latex or synthetic condom plus diaphragm or cervical/vault cap with spermicide.

NOTE: All females will be considered to be of childbearing potential unless they are postmenopausal (amenorrheic for at least 12 consecutive months, in the appropriate age group, and without other known or suspected cause) or have been sterilized surgically (ie, bilateral tubal ligation, total hysterectomy, or bilateral oophorectomy, all with surgery at least 1 month before dosing).

14. Be considered inappropriate for evaluation in the investigator's judgment
15. Have participated in a study involving administration of an investigational drug or device within 28 days before Visit 1, or within approximately 5 half-lives of the previous investigational drug, whichever is longer
16. Have a prolonged QTcF interval (>450 ms) 2 or more times as demonstrated by a repeated electrocardiogram (ECG)

17. Have a vagal nerve stimulation (VNS) device implanted less than 5 months before Visit 1 or changes in stimulation parameters less than 28 days before Visit 1

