9.5.1.5.7 ELECTROCARDIOGRAMS

Twelve-lead electrocardiograms will be obtained as designated in the Schedule of Procedures/Assessments (Table 2) after the subject has been resting for 5 minutes. The

investigator will record the presence or absence of any ECG abnormalities (Normal/Abnormal, Not Clinically Significant/Abnormal Clinically Significant) based on the relevant ECG findings in the CRF.

In the Pretreatment Phase, only if the QTcF interval is more than 450 ms, an additional 2 consecutive ECGs separated by 5 or more minutes will be recorded.

An ECG abnormality may meet the criteria of an AE as described in this protocol (see Section 9.5.1.5.1). In these instances, the AE corresponding to the ECG abnormality will be recorded on the Adverse Events CRF.

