9.7.1.8 Safety Analyses

The safety analyses will be performed on the Safety Analysis Set.

Safety data will be summarized using descriptive statistics (eg, n, mean, SD, median, minimum, and maximum for continuous variables; n [%] for categorical variables). Safety variables include AEs, clinical laboratory parameters (biochemistry, hematology, and urinalysis), vital signs, weight, and 12-lead ECG results.

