11.4 Recording of Data

A CRF is required and must be completed for each subject who has consented/assented to participate in the study by qualified and authorized personnel. All data on the CRF must reflect the corresponding source document, except when a section of the CRF is itself used as the source document. Any correction to entries made on the CRF must be documented in a valid audit trail where the correction is dated, the individual making the correct is identified, the reason for the change is stated, and the original data are not obscured. Only data required by the protocol for the purposes of the study should be collected.

The investigator must sign each CRF. The investigator will report the CRFs to the sponsor and retain copies of the CRFs.

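### ECG safety is recorded and analysed only as the investigator's three-level interpretation, so a moderate QTcF change between baseline and Day 4 (predose) or follow-up could go unreported

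*Protocol*

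**What the plan says.** Safety and tolerability are the primary objective (Protocol 8.1), and 9.7.1.1 lists the 12-lead ECG among the safety endpoints.

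- **Recording.** Under 9.5.1.5.7 the "investigator will record the presence or absence of any ECG abnormalities", on three levels: normal, abnormal but not clinically significant, abnormal and clinically significant. No interval is named for the CRF.
- **Analysis.** Section 9.7.1.8.5 reads: "Shift tables will present changes from baseline in ECG interpretation (categorized as normal; abnormal, not clinically significant; and, abnormal, clinically significant) by visit". Section 9.7.1.8.6 plans no other safety analyses. The general statement in 9.7.1.8 is: "Safety variables include AEs, clinical laboratory parameters (biochemistry, hematology, and urinalysis), vital signs, weight, and 12-lead ECG results". It names no interval.
- **QTcF before dosing.** Exclusion criterion 16 (9.3.2) removes subjects with QTcF above 450 ms on two or more readings. Section 9.5.1.5.7 adds: "In the Pretreatment Phase, only if the QTcF interval is more than 450 ms, an additional 2 consecutive ECGs" are taken.
- **Schedule.** Table 2 places ECGs at screening, Day -1, Day 4 and the Follow-up Visit, and at unscheduled or early discontinuation visits. Note m makes the Day 4 ECG predose.
- **Limit on collection.** Section 11.4: "Only data required by the protocol for the purposes of the study should be collected".

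**The concern.** The protocol treats QTcF as important enough to decide eligibility, then names no further use for it. From that point the ECG endpoint rests on a three-level opinion given by an investigator who knows the treatment. A continuous reading that already exists on each tracing is reduced to a category that moves only when someone decides to move it.

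A subject whose QTcF goes from 405 to 448 ms has changed by 43 ms, stays under the only QTcF limit in the protocol, and can be labelled normal at both visits. A common rise of 10 ms across the group could leave the shift table unchanged. In a study whose main purpose is safety after a change of route, the report could then be silent on an interval change that its own tracings contain.

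**Working it through.** The protocol has no ECG figure to reproduce. The 20 subjects in 9.7.2 are set by feasibility, and no SD, effect size or power is given.

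**1. ECG beside the neighbouring safety measures**

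| Measure | Named for recording | Named for analysis |
|---|---|---|
| Laboratory | Numeric results (9.5.1.5.4) | Values, change from baseline and shift tables (9.7.1.8.3) |
| Vital signs, weight | Numeric values on the CRF (9.5.1.5.5) | Descriptive statistics and change from baseline (9.7.1.8.4) |
| 12-lead ECG | Three-level interpretation (9.5.1.5.7) | Shift table of that interpretation (9.7.1.8.5) |

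Only for the ECG does the plan name a category and no number.

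**2. Can the SAP repair this alone?** It can add tables, but only from data in the database. Section 9.5.1.5.7 names the label, and 11.4 discourages collecting what the protocol does not require. If no interval reaches the CRF, there may be nothing for the SAP to summarise.

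**3. What the label can miss.** The protocol does not tie the label to a QTcF value, so crossing 450 ms serves here as a stand-in for a visible change. Assumptions, none from the documents: baseline QTcF is normal, truncated at 450 ms, with mean 400 to 420 ms and between-subject SD 15 to 20 ms; every subject shifts by s.

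Chance that a subject crosses: p = [F(450) − F(450 − s)] / F(450). Expected number = 20p. Chance that nobody crosses = (1 − p)^20.

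| s | Mean, SD (ms) | p | Expected of 20 | Nobody crosses |
|---|---|---|---|---|
| 10 ms | 400, 15 | 0.0034 | 0.07 | 93% |
| 10 ms | 410, 20 | 0.0451 | 0.90 | 40% |
| 10 ms | 420, 20 | 0.0984 | 1.97 | 13% |
| 20 ms | 400, 15 | 0.0223 | 0.45 | 64% |
| 20 ms | 420, 20 | 0.2590 | 5.18 | 0.2% |

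A moderate shift may leave no trace. A larger one may partly surface, provided the investigator reclassifies the tracing or reports an adverse event.

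**4. What numeric values would give.** The 95% confidence half-width for a mean change with n = 20 is t(0.975, 19) × SD / √20. For an assumed SD of change of 10, 15 or 20 ms this is 4.7, 7.0 or 9.4 ms.

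**5. What the existing tracings can show.** For a subject who completes treatment, the only scheduled ECG during intravenous dosing is Day 4, predose. The next is at follow-up, after the return to oral perampanel on Day 5. The post-infusion PK sample, by contrast, is taken within 5 minutes of the end of infusion (Table 2, note i). Numeric QTcF at the present times would describe trough and post-switch-back values, not the end of infusion.

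**The case against.** **This is SAP material.** Section 9.7.1 leaves further detail to the SAP, and 9.7.1.8 promises descriptive statistics for safety data including ECG results. Nothing forbids a QTcF table. That is fair for the table, but it does not settle whether the values are collected.

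**The CRF wording is not conclusive.** The sentence in 9.5.1.5.7 goes on to mention the underlying ECG findings and the CRF, and can be read as meaning that the findings are entered too. Section 11.3 counts automated instrument output among source documents, so tracings may be retained at site. The protocol therefore does not say that intervals are thrown away, but neither does it require them in the database.

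**A QTcF effect would not be wholly invisible.** A reader might infer that it would. The documents do not support that: a marked prolongation can change the category, and 9.5.1.5.7 allows an ECG abnormality to be reported as an adverse event, which would reach the tables in 9.7.1.8.2.

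**Peak exposure.** A reader might also argue from Section 9.2, where single-dose intravenous Cmax fell outside the bioequivalence criteria. The same section reports a model estimate that steady-state Cmax after 30- and 60-minute infusions meets them, and subjects here have been on stable oral dosing for at least 28 days. The scheduled ECGs would not capture a peak effect in any case. The point does not rest on Cmax, and no part of the protocol reports a QT effect of perampanel.

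**A mean change is weak evidence.** With one arm and a baseline screened on QTcF, a mean change cannot be separated from regression to the mean. This stands; the summary would be descriptive. Nor should its half-width be set against the 16.8% upper limit that follows from 0 of 20 category shifts. These are different quantities, and that limit applies to any zero count in 20, including a zero count above 450 ms.

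**Conclusion.** The point holds in a limited form and should be corrected. The only ECG item named for the CRF and the only ECG analysis named are the unblinded three-level interpretation, although QTcF is read for eligibility and comparable safety measures are summarised numerically. A moderate or mean QTcF change from baseline to Day 4 predose or to follow-up could go unreported.

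The size depends on assumed distributions: for a uniform 10 ms rise, the chance that nobody crosses 450 ms runs from 93% to 13%. Numeric values would estimate the mean change to within about 4.7 to 9.4 ms for assumed SDs of 10 to 20 ms. No sample size or power figure is affected. Even when corrected, the study would say nothing about QTcF at the end of infusion.

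**What to change.** 1. In 9.5.1.5.7, require QTcF, heart rate, PR and QRS from each scheduled tracing to be entered on the CRF. This also removes the ambiguity about what is captured.
2. In 9.7.1.8.5, add descriptive statistics for values and change from baseline by visit, and the number of subjects with postbaseline QTcF above the protocol's own 450 ms limit. Keep the interpretation shift table.
3. State there that the Day 4 ECG is predose and the follow-up ECG comes after the return to oral dosing, so these summaries describe trough and post-switch-back values and cannot exclude an end-of-infusion effect. Without this, an unremarkable table could reassure more than it should.

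The cost is a few CRF fields from tracings already obtained and one extra table. No additional ECGs are needed.
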